3 CONDUCT OF STATISTICAL ANALYSIS

The statistical analyses including reformatting datasets and derivation of outcomes data-management will be carried out by numerics data gmbh, [REDACTED] (i.e. subcontractor).

The speech understanding data will be collected as % correct for either in-quiet or in-noise environments, or speech reception threshold in dB SNR for an in-noise environment.

Electrode location due to proximity to the modiolus, along with duration of deafness and age at onset of hearing loss, will be used as potential variables for the speech understanding. Therefore different categories will be implemented separating patients with a duration of ≤ 30 and > 30 years of age; onset of hearing loss at ≥ 5 and < 5 years of age, close proximity to the modiolus and distanced from the modiolus at the basal turn.

The primary hypothesis will be tested using a one sample (paired) t-test with the difference of the 6 month values versus the baseline values as outcome. This will be done for % speech understanding and dB threshold values. Results will be reported with mean and a 95% CI. The analysis will also be complemented by an analysis of covariance approach, that is, the pre-treatment values are treated as covariate while the values at month 6 are treated as outcome variable. This allows for a sensitive approach to account for baseline covariates such as age, gender and clinic, enabling meaningful average

estimates for specific subgroups with the aim to explore whether the treatment effects hold for the whole study population or are restricted to specific subgroups only. Least squares mean differences are calculated for this purpose.

The secondary hypothesis will be examined using a binomial exact test with a $p=0.8$ as H_0 reference level. This rather crude test will be complemented by regression analyses as described in section 8.2.

The analyses will be carried out with the SAS software (SAS Version 9.4, SAS Institute, Cary, NC, U.S.A.).

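### The SAP specifies duration of deafness and age at onset only as two-group variables, which costs power in the complementary models if their effects are roughly linear

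*SAP*

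**What the plan says.** SAP section 3 names electrode location as an explanatory variable and adds that it, "along with duration of deafness and age at onset of hearing loss, will be used as potential variables for the speech understanding". The next sentence turns all three into categories. For duration, "separating patients with a duration of ≤ 30 and > 30 years of age"; for onset, "onset of hearing loss at ≥ 5 and < 5 years of age"; for electrode position, "close proximity to the modiolus and distanced from the modiolus at the basal turn". No rationale for the cuts, no continuous version and no expected group sizes appear in the SAP or the protocol.

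The first primary hypothesis is tested without covariates: "The primary hypothesis will be tested using a one sample (paired) t-test with the difference of the 6 month values versus the baseline values". The second uses an exact binomial test, also without covariates. Covariates enter in the complementary ANCOVA, for which age, gender and clinic are given as examples, and in the regression models of SAP section 8.2, which leave the list and form of baseline covariates open. One stated aim of the ANCOVA is to "explore whether the treatment effects hold for the whole study population or are restricted to specific subgroups only".

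**The concern.** The SAP justifies its covariate models by their sensitivity. Reducing a variable measured in years to two groups works against that. Patients deaf for 1 year and for 29 years are treated as the same, while those at 29 and 31 years are treated as different. ANCOVA and the SAS procedures named in section 8.2 all accept continuous covariates.

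At stake is the ability to see whether duration and onset are associated with speech understanding. Protocol section 9 says that the OLSA and HSM noise tests cannot be converted into one another, so the number of patients for a given noise test may be well below 150, leaving less power to spare.

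The duration label adds a smaller problem: it gives a duration in years of age. Read literally, a programmer could split on the patient's age instead of years of deafness. One validation method in SAP section 4 is reprogramming from the SAP, which could carry the ambiguity into the check.

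**Working it through.** **Inputs from the documents.** N = 150 and two-sided alpha 0.05 (SAP section 2); cuts at 30 and 5 (SAP section 3); SD of the paired difference 3.0 and mean difference 1.0 (SAP Table 1). The documents give no distribution for either variable, no split and no effect size, so those below are assumptions.

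**Step 1: the plan's own figures.** The documents state no figure for information loss. Their stated powers at N = 150 reproduce:
- Table 1, paired t-test, noncentral t with 149 df and noncentrality √150 × 1.0/3.0: 0.9820 (stated 0.98196).
- Table 2, exact McNemar: 0.999 (stated 0.999).
- Table 3, exact binomial, 0.80 against 0.90, rejecting at ≤109 or ≥130: 0.9279 (stated 0.9279).

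None of these depends on the two-group cuts.

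**Step 2: information kept by a two-group cut.** For a linear effect, the share kept is the squared correlation between the variable and its two-group version. With p the share of patients above the cut:
- Normal: φ(z)²/[p(1−p)], with z the normal quantile at 1−p
- Exponential: (ln p)² × p/(1−p)
- Uniform: 3p(1−p)

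| Share above cut | Normal, lost | Exponential, lost | Uniform, lost |
|---|---|---|---|
| 50% | 36.3% | 52.0% | 25.0% |
| 30% | 42.4% | 37.9% | 37.0% |
| 20% | 51.0% | 35.2% | 52.0% |
| 10% | 65.8% | 41.1% | 73.0% |

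The smallest possible loss is 36.3% for a normal variable and 35.2% for an exponential one. For a uniform variable, the loss is above one third only when the smaller group holds less than a third of patients.

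**Step 3: age at onset as a mixture.** Onset may cluster in early childhood. A simulation took 10% to 50% of patients as uniform over 0–5 years and the rest as normal truncated below 5, with mean/SD of 40/15, 50/10 or 30/18. The loss ran from 8% (half early, 50/10) to 72% (10% early, 30/18).

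**Step 4: power for the association.** Assume a true correlation r = 0.25. By Fisher's z, power = Φ(atanh(r√k) × √(N−3) − 1.96), with k the share of information kept.

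| Form | k | Power, N = 150 | Effective N (150k) |
|---|---|---|---|
| Continuous | 1 | 87.2% | 150 |
| Normal, 50/50 | 0.637 | 68.9% | about 96 |
| Normal, 20/80 | 0.490 | 57.3% | about 74 |

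At r = 0.20 the three powers are 69%, 50% and 40%; at r = 0.30 they are 96%, 84% and 73%.

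**Step 5: precision of adjusted means.** This is a different quantity. Residual SD is proportional to √(1 − r²k). At r = 0.25:
- Continuous: √(1 − 0.0625) = 0.968
- 50/50: √(1 − 0.0625 × 0.637) = 0.980, so standard errors are about 1.2% wider
- 20/80: about 1.7% wider
- 10/90: about 2.2% wider

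Even at r = 0.5, a 50/50 cut costs about 6%.

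**The case against.** The strongest reply is that the categories serve a stated purpose. The SAP wants estimates for specific subgroups, and cuts fixed in advance provide them and prevent cut-points chosen from the data. That stands, so a reader should not infer that the cuts bring no benefit. It is a reason to keep them, but not a reason to make them the only form.

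Second, the SAP does not say that the two variables enter the models only as categories, since section 8.2 leaves covariate form open. This is fair: a continuous term is not ruled out. But the two-group form is the only one written down, and an analyst following the SAP would use it.

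Third, the documents do not say that duration and onset are recorded in years. The protocol mentions medical history taken from hospital files, and no CRF is available. Cuts at 30 and 5 imply that years are known at least approximately, but the remedy has to be conditional on that.

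Fourth, one might infer that differences between clinics in these variables are left largely unadjusted. The SAP names clinic as an ANCOVA covariate, which absorbs mean differences between clinics, and the main contrast is within patient.

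**Conclusion.** The point holds as a low-severity improvement. Both variables are specified only in two groups, without a rationale. If the effect is roughly linear, the complementary models have less power to detect their association with speech understanding: at an assumed correlation of 0.25 and N = 150, about 87% continuous against 69% (normal covariate cut at the median) or 57% (20/80).

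Two stronger readings are not supported. A reader might infer that a third or more of the information is always lost. That needs a roughly normal or exponential variable with a linear effect. A uniform variable cut at its median loses 25%, onset mixtures lose 8% to 72%, and if the true effect is a step at the cut, nothing is lost. The figure is firmer for duration than for onset. A reader might also carry the 36% to 51% loss over to the adjusted means, but their standard errors widen by only about 1% to 2% at the same correlation.

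The primary tests, their stated power and the sample size are unaffected. The ambiguous duration label needs correcting whatever is decided about the cuts.

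**What to change.** In SAP section 3, with a matching line in section 8.2:
- Where years are recorded, enter duration of deafness and age at onset as continuous terms in the ANCOVA and regression models. Use linear terms, or a 3-knot spline if the residual diagnostics already planned show curvature.
- Keep the pre-specified categories for descriptive tables and the planned subgroup estimates, with a sentence justifying each cut.
- Reword the 30-year cut so that it refers to years of deafness.

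The cost is SAP wording, one model degree of freedom per variable for a linear term or two for a 3-knot spline, and a little more analysis work. No new data are needed if years are on file.

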4 QUALITY CONTROL ON STATISTICAL ANALYSIS

The quality control of the statistical analyses will be conducted according to the SOPs of the subcontractor numerics data gmbh.

The method of validation is based upon the criticality level which is a combination of the complexity of the underlying SAS program and the impact of errors (importance of delivery):

1. Method 1: Reprogramming on the basis of the study specification, or on the basis of the requirements according to the study SAP.
2. Method 2: Review of the programming code based on the SAS Programming Standards and study specifications.
3. Method 3: Validation of output listings on the basis of the corresponding raw datasets (i.e. spot checks of selected data).
4. Method 4: Validation of results against the listings or related tables.

Code review and output review will be carried out by an independent person (i.e. not identical to the primary programmer).

5 DERIVED DATA

Derived data will include the binary response as a difference between baseline (pre-op) and 6 months post-operative visits, respectively. A response ($y=1$) will be defined as better speech understanding with respect to pre-op, a non-response ($y=0$) will be defined as a worse or equal speech understanding. In addition, paired differences of pre-op values vs. month 6 will be carried out.

6 PRESENTATION OF DATA

Tables will include data for continuous variables and discrete variables.

Continuous variables will be reported presenting: n, mean, stdev, median, a 95 % confidence interval (CI), a 25% and 75% percentile along with a minimum and maximum value.

Discrete variables will be presented showing the counts along with %-ages and a 95 % CI.

Specific tables will be produced for the regression model results containing information about model fitness, degrees of freedom etc.

Figures include box-plots, scatter-plots and mean +/- standard error plots of differences for visits pre-op, month 3 and month 6. Moreover, profile plots of averages of electrode impedances over the electrode contact location range will be produced. Likewise, profile plots will be produced to illustrate the hearing thresholds over the respective frequency ranges.

All figures and tables/listings will be produced as rtf-files allowing for implementing in MS WORD.

7 ANALYSIS POPULATIONS

ITT: the intention to treat population will comprise all patients with a baseline assessment.

PP: the per-protocol will include only patients with a non-missing assessment at pre-op and at visit 3 months or 6 months.

8 EFFICACY ANALYSIS

8.1 Tables, figures and lists

Demographic section

Age and gender distribution by center and overall.

Efficacy outcomes

Descriptive tables of the various outcome variables in the format described under chapter 6 Presentation of data.

Specific tables summarizing the results of the regression analysis (see section below) with estimates +/- standard error of the time effects (visits) and covariates.

Note that time effects will be considered as treatment effects (visit 3 and visit 6 against visit pre-op).

8.2 Statistical methods

Hypothesis testing

Formal testing of the 1st primary hypothesis claiming a difference of 20% or more for speech understanding will be carried out by using a paired t-test on differences of speech understanding (i.e. values at visit 6 months - values at pre-op) with a reference proportion of 20%. Number of patients with values greater or less than 20% will be reported.

Formal testing of the 2nd primary hypothesis claiming an improvement of 80% or more of patients showing post-operative improvement will be carried out by using a binomial test (one-sample) of improvement rates with a reference proportion of 80%.

These tests will be carried out at the final analysis only. For interim analyses, descriptive rates along with 95% confidence levels will be produced reporting the frequencies of responses along with the 95% CI based on exact methods (Clopper-Pearson) for visits pre-op, month 3 and month 6.

At the final analysis, in addition refined analyses will be carried out based on a modeling approach. This enables a more sensitive analysis allowing for covariates (such as baseline characteristics). Regression analyses will be carried out for this purpose incorporating the paired structure of observations. To this end the SAS proc genmod will be used (procedure glimmix will be used as a sensitivity analysis as it estimates random effects using a different approach). Furthermore, this modelling approach allows for:

- estimating consolidated treatment effects comparing post-baseline vs. pre-op performance.
- considering center specific deviations from the thresholds used by keeping these threshold as covariate for the binomial response (success rate).

Analyses will be carried out both based upon the ITT population and the PP set. Due to the nature of the data, i.e., paired data analyses based upon ITT, this will be considered as secondary and carried out in the perspective of a sensitivity analysis. For this purpose a random effects model is required to be used treating the patient as random effect.*.

* Brown, H. & Prescott, R. (1999). *Applied Mixed Models in Medicine*, New York: John Wiley & Sons.

Analyses based on continuous outcomes such as audiometric thresholds or electrode impedances will be carried out in a similar manner using the SAS proc mixed to account for random effects of normally distributed data.

Special care will be directed to check for model adequacy by examining the residual diagnostics (specific figures to this end will be presented in the appendix section of the report).

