1.3 Hypotheses

1.3.1 Primary hypotheses of retrospective study

1. H_0 : Speech understanding in quiet and in noise at the 6 months post-operative visit are equal with speech understanding in quiet and noise at the pre-operative evaluation visit
 H_1 : Speech understanding in quiet and in noise at the 6 months post-operative visit is better than speech understanding in quiet and noise at the pre-operative evaluation visit
2. H_0 : The proportion of the recipient's cohort examined showing post-operative improvement per test and listening condition is below 80% for the 6 months post-operative visit.
 H_1 : The proportion of the recipient's cohort examined showing post-operative improvement per test and listening condition is $\geq 80\%$ (Dowell, Hollow & Winton, 2004) for the 6 months post-operative visit.

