2.1 Sample size calculation

For the 1st primary hypothesis about speech understanding a power calculation was carried out to estimate the ability to detect a difference amounting to 20% for a clinically relevant benefit with the Freiburger monosyllabics test between the pre-op evaluations and 6 months evaluation covering test-/retest-variability and the respective deviation. For speech understanding in noise the clinically relevant difference between pre-op evaluation and 6 months visit is expected to be 1,4 dB SNR-SRT for OLSA, 30% for HSM.

A sample of $n=150$ patients is deemed sufficient to detect meaningful differences based on dB threshold values and % correct values. The standard deviation of the difference is based upon an earlier OLSA study (CAG5149 MP3000 Optimization Trial) and assumed as 3.0 to be on the conservative side.

Table 1: Numeric Results for Paired T-Test

Null Hypothesis: Mean of Paired Differences = 0, Alternative Hypothesis: Mean of Paired

Differences ≠ 0

Power	N	Alpha	Beta	Mean of Paired Differences	S	Effect Size
0.91002	100	0.05000	0.08998	1.0	3.0	0.333
0.95888	125	0.05000	0.04112	1.0	3.0	0.333
0.98196	150	0.05000	0.01804	1.0	3.0	0.333

Source for the study parameters:

ACE OLSA Data taken from MP3000 trial:

n=58, stdev.=3.3, rho=0.76, => stddev_diff = 2.29

$$\sigma_d = \sqrt{\sigma_1^2 + \sigma_2^2 - 2\rho\sigma_1\sigma_2}$$

To test for an improvement of 20% (0.2) in speech understanding, as compared to baseline, a reference proportion of 50% (0.5) and a correlation within patient of rho=0.5 is assumed. Based upon a sample of n=150 patients, the power to detect such a difference amounts to 99.9%, c.f Table 2.

Table 2: Power estimation using McNemar exact test for paired proportions

The POWER Procedure, McNemar Exact Conditional Test

Fixed Scenario Elements	
Distribution	Exact conditional
Method	Exact
Proportion 1	0.5
Proportion 2	0.7
Correlation	0.5
Number of Sides	2
Null Ratio of Discordant Proportions	1
Nominal Alpha	0.05

Computed Power			
Index	N Pairs	Actual Alpha	Power
1	100	0.0300	0.981
2	125	0.0322	0.995
3	150	0.0348	0.999

For the 2nd primary hypothesis claiming that the proportion of patients showing post-operative improvement is ≥80%, this translates into a one-sample test with a null hypothesis reference level of 80% (i.e. 0.8).

Table 3: Numeric Results for testing $H_0: P = P_0$ versus $H_1: P \neq P_0$, 2-sided: Exact Test

Power	N	Proportion	Proportion	Difference (P1 - P0)	TargetActual		Reject H0 If	

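### SAP 8.2 tests hypothesis 1 against a 20% gain, but the stated H0 and its power tables use no change; if the true gain is 20 points, success is 2.5%, not 99.9%

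*SAP*

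**What the plan says.** Protocol 7.3.1 and SAP 1.3.1 give the same null for hypothesis 1: speech understanding "at the 6 months post-operative visit are equal with speech understanding in quiet and noise at the pre-operative evaluation visit". The alternative is that it is better at 6 months.

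SAP 2.1 follows that null. Table 1, for the paired t-test, is headed "Null Hypothesis: Mean of Paired Differences = 0". Table 2, an exact McNemar calculation, uses a null discordant ratio of 1, which is again no change. Here 20% is the effect to be found: for a move from 0.5 to 0.7 with n=150, "the power to detect such a difference amounts to 99.9"%. The same section ties 20% to the Freiburger monosyllables in quiet. For the noise tests it says the relevant difference "is expected to be 1,4 dB SNR-SRT for OLSA, 30% for HSM".

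SAP section 3 describes a paired t-test of 6-month against baseline values, for percent scores and for dB thresholds, and names no 20% reference.

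SAP 8.2, under its hypothesis-testing heading, departs from this. It begins "Formal testing of the 1st primary hypothesis claiming a difference of 20% or more for speech understanding" and specifies the t-test on differences ("values at visit 6 months - values at pre-op) with a reference proportion of 20"%). The next paragraph handles hypothesis 2 with a "binomial test (one-sample) of improvement rates with a reference proportion of 80"%.

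**The concern.** A null of no change and a null of a 20-point gain are different hypotheses, and the SAP contains both for the same primary question. Nothing in either document says which one governs. An analyst programming from 8.2 would set the null at 20. One working from section 3 or from the stated H0 would set it at 0. The two can give opposite answers on the same data, so the choice could be made after the results are known.

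The power statement is also detached from the test. The 20% that SAP 2.1 sets out to detect is the value 8.2 has to exceed, so the quoted power cannot belong to the 8.2 test.

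Finally, hypothesis 1 covers quiet and noise. A 20% reference has no meaning for OLSA, which is scored in dB SNR. If applied to HSM, it disagrees with the 30% in SAP 2.1.

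**Working it through.** **Inputs from the documents.** n=150 and two-sided alpha 5% (SAP section 2); difference to detect 20 points, proportions 0.5 and 0.7, within-patient correlation 0.5 (SAP 2.1); SD of the paired difference 3.0 for OLSA (SAP 2.1); reference value 20 (SAP 8.2).

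**Assumed.** The SAP gives no SD for paired differences in percent scores. I use 20, 25 and 30 points, with normally distributed differences and all 150 patients contributing.

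**Step 1: reproduce the plan's figures.**

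- *Table 1.* Noncentrality = (1.0/3.0)·√150 = 4.08 on 149 df. Power from the noncentral t is 0.98196, as stated. The rows for n=100 and n=125 also match (0.91002, 0.95888).
- *Table 2.* Probability of success at both times = 0.5·0.7 + 0.5·√(0.5·0.5·0.7·0.3) = 0.35 + 0.1146 = 0.4646. The discordant cells are 0.5 − 0.4646 = 0.0354 and 0.7 − 0.4646 = 0.2354. Exact conditional McNemar power is 0.981, 0.995 and 0.999 at n=100, 125 and 150, as stated.

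Both tables are correct for a null of no change. Table 2 concerns a binary outcome, so it is not the power of a t-test on percent scores under either null.

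**Step 2: change the null to 20 and keep the true gain at 20.** For true mean gain δ and null value δ₀, the noncentrality is (δ − δ₀)·√n/SD. With δ = δ₀ = 20 it is 0 whatever the SD or n. The chance of a significant result in the favourable direction is then the upper-tail alpha, 2.5%; total two-sided rejection is 5%. A simulation of 100,000 trials with SD 25 gave 2.4% and 4.9%.

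**Step 3: the same true gain against a null of 0.** Noncentrality = 20·√150/SD, which is 8.2 even at SD 30. Power exceeds 99.9% for SDs of 20 to 30.

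**Step 4: true gains on either side of 20, n=150.**

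| Assumed SD (points) | True gain 15: 8.2 test significantly below 20 | True gain 25: 8.2 test significantly above 20 | True gain needed for 80% power against 20 |
|---|---|---|---|
| 20 | 86% | 86% | 24.6 |
| 25 | 68% | 68% | 25.7 |
| 30 | 53% | 53% | 26.9 |

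The middle columns agree because 15 and 25 lie equally far from 20. The last column is 20 + (1.96 + 0.842)·SD/√150; for SD 25, 20 + 2.802·25/12.247 = 25.7. Against a null of 0, a true gain of 15 has noncentrality 15·12.247/30 = 6.1 at SD 30, and power above 99.9%.

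**Step 5: is 20% really the null in 8.2?** The paragraph on hypothesis 2 uses the same construction for 80%. SAP 2.1 and section 3 both identify 80% as the H0 value. The count of patients above and below 20% is a separate sentence in 8.2, so the reference value belongs to the t-test.

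**The case against.** The best defence is that 8.2 is loosely worded. A paired t-test has no reference proportion, and the sentence that follows uses 20% as a per-patient threshold, so the phrase may be a misplaced relevance criterion. Section 3 already promises a paired comparison with a mean and 95% CI, from which equality can be judged. The wording is indeed ambiguous, but the parallel with the 80% null and the statement that the hypothesis claims at least 20% favour the literal reading. The confidence interval does not settle which null decides the primary hypothesis.

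A second objection is that 2.5% is a truism: any test succeeds at its tail alpha when the truth equals its null. SAP 2.1 presents 20% for the Freiburger test as a clinically relevant difference, not a forecast, and a much larger true gain would still pass. This is correct and limits the claim to true gains near or below the mid-20s. But 20% is the effect for which the SAP claims 99.9% power, so the comparison is with its own planning value.

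Third, if the 20% in 8.2 is meant for the Freiburger test alone, it does not conflict with the HSM figure. In that case 8.2 gives no reference value for either noise test, although hypothesis 1 includes them.

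Fourth, the use of McNemar in Table 2 is a separate defect that would exist without the 8.2 wording. That is so; it matters here because Table 2 is the source of the 99.9%.

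**Conclusion.** The concern holds. The formal test in SAP 8.2 contradicts the H0 in both documents, Tables 1 and 2, and the plain paired t-test in SAP section 3. At a true mean gain of 20 points the 8.2 test succeeds 2.5% of the time; this needs no assumption about SD or n. Against a null of 0, power for the same gain is above 99.9% for SDs of 20 to 30 points. The other figures (24.6 to 26.9 points needed for 80% power; a 53% to 86% chance of landing significantly below 20 when the true gain is 15) rest on that assumed SD range and on n=150 for the test concerned. Table 3 is not affected, since it serves hypothesis 2. This must be fixed before the final analysis, because the choice of null determines what the study may conclude on its first primary hypothesis.

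**What to change.** State one null for hypothesis 1 in SAP 1.3.1, 2.1, 3 and 8.2. The simplest route that agrees with the protocol is:

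- In 8.2, test the mean paired difference against 0 separately for each speech test.
- Use 20 points (Freiburger), 1.4 dB (OLSA) and 30 points (HSM) only as benchmarks for reading the 95% CI, and keep the count of patients above and below 20% as description.
- Replace Table 2 with a paired t-test power calculation for percent scores, with a stated and sourced SD.

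If the sponsor does want to show a gain beyond a margin, H0 and H1 must be rewritten in the protocol and the SAP, a margin set for each test in its own units, and the power recalculated for a true gain above that margin.

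The first route costs some SAP wording and one recalculated table. The second also needs a protocol amendment. Neither requires new data or patients. How the quiet and noise results combine into one conclusion is a separate question that this change leaves open.

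### The binary response means improvement over pre-op, yet it is tabulated at pre-op and its regression is to be read through visit effects against pre-op, which then have no finite estimate

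*SAP*

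**What the plan says.** **Definition.** SAP section 5: "Derived data will include the binary response as a difference between baseline (pre-op) and 6 months post-operative visits". A response "will be defined as better speech understanding with respect to pre-op", and a non-response "will be defined as a worse or equal speech understanding". The SAP defines no other binary outcome, and this one is defined for 6 months only.

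**Tabulation.** For interim analyses, SAP section 8.2 reports response frequencies with 95% intervals "based on exact methods (Clopper-Pearson) for visits pre-op, month 3 and month 6".

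**Regression.** SAP section 3 says of the exact binomial test against 0.8: "This rather crude test will be complemented by regression analyses as described in section 8.2". Section 8.2 describes models in PROC GENMOD, with GLIMMIX as sensitivity analysis, that keep the pairing of observations. One listed purpose is "estimating consolidated treatment effects comparing post-baseline vs. pre-op performance". Another refers to "keeping these threshold as covariate for the binomial response (success rate"). Section 8.1 adds, for the regression tables: "Note that time effects will be considered as treatment effects (visit 3 and visit 6 against visit pre-op").

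**The concern.** A pre-op score compared with itself is equal, so under section 5 every pre-op record is a non-response, unless the response is taken not to exist there. Either way, a response rate at pre-op carries no information, and an odds ratio against a reference visit made up only of zeros cannot be estimated.

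Pre-op rows do appear intended for the model. Section 8.1 names pre-op as the reference visit, and section 8.2 asks for a paired structure, whereas one improvement indicator per patient has nothing to pair. SAP section 7 also admits to the ITT set anyone with a baseline assessment. A patient with only that assessment can contribute only a pre-op row.

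At stake is the covariate-adjusted support for the second primary hypothesis. The SAP has no rule for separation, so the programmer would have to choose another outcome or model with the data in hand. Even a finite effect against pre-op would not say whether the improvement rate reaches 80%.

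**Working it through.** **1. The plan's own figure.** SAP Table 3, N = 150, rejection if the count is ≤109 or ≥130:
- Actual alpha = P(X ≤ 109) + P(X ≥ 130) at p = 0.8, which is 0.0411.
- Power, by the same sum at p = 0.9, is 0.9279.

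Both agree with the table. This one-sample test uses one response per patient and no pre-op row.

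**2. The pre-op row.** The count is 0/n by construction. The Clopper-Pearson upper limit is 1 − 0.025^(1/n). Protocol section 8.1 places the first export after 50 datasets. If all 50 contribute, the row reads 0/50 with 95% CI 0 to 7.1%, because 1 − 0.025^(1/50) = 0.071. The interval depends on n alone.

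**3. Why the contrast diverges.** Assume a logit link (the SAP states none), with b0 the pre-op intercept and b3, b6 the visit effects. The likelihood is the pre-op part times a post-operative part that depends on b0 + b3 and b0 + b6. With n pre-op zeros and no covariates, the pre-op log-likelihood is n·ln(1 − expit(b0)). For n = 150:
- b0 = −2: −19.04
- b0 = −5: −1.007
- b0 = −10: −0.0068
- b0 = −20: −0.0000003

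It always gains from a lower b0. Raising b3 and b6 by the same amount leaves the post-operative part unchanged. So b0 runs to minus infinity, b3 and b6 run to plus infinity, and the sums b0 + b3 and b0 + b6 stay finite. This is quasi-complete separation.

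**4. Illustrative fit.** 150 simulated patients, pre-op all 0, response 0.827 at month 3 and 0.900 at month 6 (assumed rates). Logit model:

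| Iterations | b0 | b6 | SE of b6 | b0 + b6 |
|---|---|---|---|---|
| 5 | −6.564 | 8.761 | 1.3 | 2.197 |
| 10 | −11.566 | 13.763 | 16.1 | 2.197 |
| 20 | −21.566 | 23.763 | 2,386.8 | 2.197 |
| 30 | −31.566 | 33.763 | 354,235.3 | 2.197 |

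The log-likelihood flattens at −117.932. The values of b6 show only where the software stopped. The last column is constant and equals ln(0.9/0.1) = 2.197.

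- GEE fits (the GENMOD route) gave visit effects of about 32 to 42 with SEs of order 10^4 to 10^6, one of them not computable.
- A random-intercept model (the GLIMMIX route) had a profile log-likelihood still rising as b0 went from −3 (−125.22) to −20 (−117.4755). At b0 = −12, −16 and −20, b0 + b6 was 2.479 each time.

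**5. What survives.** In another illustrative fit with visit, clinic and a continuous baseline covariate, the adjusted month-6 logit was 1.881 (SE 0.244) at 10, 15, 20 and 25 iterations. It was the same with the pre-op rows removed. The covariate coefficient was −0.559 (SE 0.173) in both. Such a logit can be set against logit(0.8) = ln 4 = 1.386.

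**6. Two repairs, on illustrative data.**
- Post-operative rows only (GEE): month 6 versus month 3 log-odds 0.64 (SE 0.33), and month-6 logit 1.562 + 0.635 = 2.197, as before.
- A status that can be 0 or 1 at every visit, using the 0.5, 0.7 and correlation 0.5 of SAP Table 2: post versus pre-op log-odds 0.75 (SE 0.16).

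**The case against.** The strongest reply is that no single sentence puts the section 5 response on pre-op rows. Section 5 gives one value per patient. The visit contrast in section 8.1 covers the various outcomes and is sound for scores. The first modelling purpose in section 8.2 speaks of performance, and the binomial response appears in a separate bullet. SAP section 2.1 works with paired proportions of 0.5 and 0.7, and section 8.2 mentions thresholds, so a visit-level success status may have been meant. That would not separate. This stands as a possible intention, but the SAP never defines such a status, and section 3 ties the section 8.2 regressions to the improvement test. The pre-op row in the interim table is explicit in any case.

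A reader might also infer that the whole regression fails and cannot adjust the 80% conclusion for clinic or baseline. The SAP does not support that. Step 5 shows that the adjusted month-6 rate and the covariate effects are unchanged by the pre-op rows; only the intercept and the visit-versus-pre-op effects are lost. Nor would an interim row read 0/150, since SAP section 2 expects 150 datasets at the final analysis.

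Finally, the regression is supplementary and the interim tables are descriptive. That limits the harm, but these contrasts are what the SAP says it will report as treatment effects.

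**Conclusion.** The point holds within limits. As written, the pre-op row of the binary table is empty of information. If pre-op rows enter the binomial model with the only response defined, the effects the SAP calls treatment effects have no finite estimate. Finite quantities that bear on the 80% question exist in the same model, but the SAP does not designate them.

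The divergence assumes a logit link and the section 5 response on pre-op rows. It does not depend on the assumed post-operative rates, because it comes from the all-zero reference visit. Under any link the pre-op rate is 0 by construction. The confirmatory exact binomial test, the paired t-test and the continuous-outcome models are untouched. The SAP should be amended before the final analysis, but the defect does not threaten the primary tests.

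**What to change.** - Drop the pre-op row from the binary response table in SAP section 8.2.
- Extend the section 5 definition to month 3, which is tabulated and modelled but not defined.
- Fit the binary improvement model to post-operative visits only, with patient as the cluster, separately per test and listening condition. Use that test's own pre-op score and clinic as covariates where estimable. One pooled model would not do: scores are in % correct or dB SNR (SAP section 3), protocol section 9 says OLSA and HSM results have no linear relation, and the second hypothesis is stated per test and listening condition.
- Name the adjusted month-6 improvement rate, with its 95% CI against 80%, as the reported result.
- Keep visit-versus-pre-op contrasts for the scores themselves.
- If a visit-level success status was intended, define it and use that outcome for the visit contrasts.

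The cost is wording in SAP sections 5, 8.1 and 8.2 and slightly different tables. No new data are needed.
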